7.2.2.3 THROMBOEMBOLIC EVENTS

Recent pre-clinical and clinical data demonstrate that MSCs can express or increase secretion of proteins associated with coagulation signals.^{49,50} However, these incident events are rare (17 events in 1112 patients in the meta-analysis³⁹), and were reported in both treatment and control groups with no significant difference associated with administration of MSCs. Thus, these events will likely be rare and as such investigators should evaluate embolic events in their differential diagnosis while managing clinical changes within 24 hours following Descartes-30 infusion.

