16.3 SCHEDULE OF ACTIVITIES

Procedures	Study Visit 1/ Screening Visit ^j	Study Visit 2/ Day 1	Study Visit 3/ Day 2	Study Visit 4/ Day 3	Study Visit 5/ Day 4-6 ^f	Study Visit 6/ Day 28 ^g
Informed consent	X					
Demographics	X					
Medical history	X					
Concomitant Medications	X	X	X	X	X	X
Clinical End-point Assessment ^a		X	X	X	X	X
Research Blood Collection ^b	X	X	X	X	X ^e	X ^f
Exploratory BAL ^c	X				X ^e	
APACHE II score ^d	X					
CBC with differential ^h	X	X	X	X	X ^e	
Serum chemistry ^{h,i}	X	X	X	X	X ^e	
CRP, ferritin, D-Dimer	X	X	X	X	X ^e	
PT/INR, PTT ^h	X	X	X	X	X ^e	
Chest X-Ray or CT Scan	X				X ^e	X

a Clinical End-Point Assessments include: Survival (Y/N), On mechanical ventilation (Y/N), In ICU (Y/N), In Hospital (Y/N), Use of anti-coagulation (drug, dose, intent: prophylaxis vs therapeutic), WHO Ordinal Score. If patient is in ICU then the following assessment will be completed: Sequential Organ Failure Assessment (SOFA), PaO₂/FiO₂, ventilation variables (See Section 6 for details), recording of vasoactive drugs and renal support, recording of supportive interventions that can impact clinical end-points (i.e., use of prone ventilation, use of paralytics, use of pulmonary vasodilators, use of corticosteroids, use of oral decontamination and raising the head of the patient to at least 30° to prevent ventilator-associated pneumonia)

b See Laboratory Manual for details of sample collection for exploratory assays.

c If not possible, use tracheal aspirates.

d See [Appendix A](#) for APACHE II score system.

e To be done only once during this period

f If still in ICU

g Day 28 or last day of hospital, whichever comes first.

h If performed as Standard of Care

i Serum Chemistry includes Glucose, Ca, Mg, Phos, ALP, Albumin, Total Protein, Total Bilirubin, K, Na, Cl, HCO₃, BUN, Cr, ALT, AST, LDH, Amylase

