16.5 BIOMARKER ANALYSIS AND STATISTICAL CONSIDERATIONS

16.5.1 SAMPLE SIZE

Given the small study size, statistical analyses will be primarily descriptive. Results of Descartes-30 treated patients will be compared to the parallel control patients (one-sided Student's t-test for all continuous variables). Longitudinal analysis of pharmacokinetics and pharmacodynamics biomarkers and will be used to inform (1) additional cohort expansion and/or (2) statistical and power considerations for randomized trial design and inferential statistics.

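### Section 16.5.1 prescribes a one-sided t-test for every continuous variable, so for each marker a treated–control difference in one direction can never be declared significant

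*Combined protocol and SAP*

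**What the plan says.** Appendix E describes biospecimen and clinical data collection in ARDS patients, who serve as parallel controls. Its Section 16.5.1 opens: "Given the small study size, statistical analyses will be primarily descriptive". It then names one test for the comparison of treated with control patients: "Results of Descartes-30 treated patients will be compared to the parallel control patients (one-sided Student's t-test for all continuous variables"). The next sentence concerns longitudinal analysis of pharmacokinetic and pharmacodynamic biomarkers, which "will be used to inform (1) additional cohort expansion and/or (2) statistical and power considerations for randomized trial design and inferential statistics".

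The readable text gives no significance level, no direction for any variable and no reason for using one tail. Sections 16.5.2 and 16.5.3 are largely redacted, so directions may be stated there. In the main protocol, Section 9.1 describes the study objectives as non-inferential, and Section 9 names no test.

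The continuous variables scheduled in Section 16.3 include CBC, CRP, ferritin, D-dimer, PT/INR, PTT and a chemistry panel: "i Serum Chemistry includes Glucose, Ca, Mg, Phos, ALP, Albumin, Total Protein, Total Bilirubin, K, Na, Cl, HCO₃, BUN, Cr, ALT, AST, LDH, Amylase". The same laboratory variables appear in the treated patients' schedule in Section 1. Section 7.2.2.3 notes that "MSCs can express or increase secretion of proteins associated with coagulation signals".

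**The concern.** A one-sided test can be defended for a single marker with a stated expected direction. Here one rule covers every continuous variable. For sodium, potassium, calcium, glucose, blood counts and clotting times, high and low values can both matter, so neither tail alone is the right one. For D-dimer the protocol itself gives a reason to look at increases. If the tested tail is a fall, taken as benefit, a rise in treated patients relative to controls could only be reported as not significant.

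What is at stake is how informative and fair the treated–control comparison is. It carries the only test named in the readable plan. A reader of its results could not tell from the p-value whether a marker was unchanged or had moved the other way.

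**Working it through.** The plan gives no significance level, control number, effect size or power for this comparison, so there is no figure of its own to reproduce. The point is checked as a property of the test, with sizes and levels assumed where stated.

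**1. The untested direction.** Let T be the pooled two-sample t statistic, signed so that positive values lie in the tested direction. The one-sided p-value is P(t_df ≥ T). If the observed difference is in the untested direction, T < 0 and p > 0.5. It therefore cannot fall below 2.5%, 5% or 10%. This needs no assumption about sample size, and redacted text that fixes directions would not change it: each variable would still have one such side.

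**2. What a two-sided analysis would show.** Assumptions: 24 treated ARDS patients (12 in Arm 1 plus 12 in the Arm 2 ARDS cohort) and 12 controls. The number of controls is not in the readable text, so other sizes are shown. The noncentrality is δ = d / √(1/n_T + 1/n_C), with d in SD units and df = n_T + n_C − 2. For 24 v 12 and d = 1.0, δ = 1/√(1/24 + 1/12) = 2.83 and df = 34.

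| Sizes | True shift in the untested direction | Chance the one-sided test declares that shift | Two-sided 5% power |
|---|---|---|---|
| 24 v 12 | 1.0 SD | 0 | 78.5% |
| 24 v 12 | 0.5 SD | 0 | 28.0% |
| 12 v 12 | 1.0 SD | 0 | 64.9% |
| 24 v 24 | 1.0 SD | 0 | 92.4% |

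The one-sided entry is exactly zero by step 1. The test can still reject by chance in the opposite, tested direction (at one-sided 5%: 0.1% of the time for 24 v 12 and 0.5 SD; 0.003% for 12 v 12 and 1.0 SD). Those are errors of direction and should not be read as power.

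**3. Cost for benefit.** For a 1.0 SD shift in the tested direction at 24 v 12 (δ = 2.83, df = 34):

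- one-sided 5%, critical value 1.691: power 87.0%;
- two-sided 5%, critical value 2.032: power 78.5%, a loss of 8.5 percentage points;
- one-sided 2.5%, critical value also 2.032: power 78.5%, so a move to two-sided 5% loses nothing;
- two-sided 90% interval, critical value 1.691 on each side: 87.0% for benefit, and the same for harm.

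**4. Conditional note on error rate.** If a direction were chosen after seeing the data, the chance of a false positive per variable would be P(|T| > t_{1−α}) = 2α: 2.5% becomes 5%, and 5% becomes 10%. Simulation with 400,000 runs per setting, at 12 v 12, 24 v 12, 36 v 12 and 12 v 6, gave 0.0497 to 0.0501 and 0.0995 to 0.1002. With the direction fixed in advance, the rate stays at about its nominal value.

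**The case against.** The strongest reply is that little depends on this test. Section 16.5.1 calls the analyses primarily descriptive, the controls are not randomised, and the MTD endpoint does not use the comparison. Safety is handled by other routes: laboratory values and adverse events are tabulated descriptively (9.2), clinically significant laboratory abnormalities count as adverse events (8.1.1), and dose-limiting toxicity, escalation and pausing follow event rules (8.1.2, 4.4, 4.5, 8.5). All of this stands, and it limits the point to the reporting of one comparison. A reader might infer that harm in a safety marker would look the same as no effect. The documents do not support that, because such a shift would remain visible through these routes.

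Two other stronger readings also fail. A reader might infer that the test drives cohort expansion, since the two sentences are adjacent. The sentence on expansion has longitudinal biomarker analysis as its subject, and Section 4.5 makes Arm 2 enrolment depend on the medical monitor's review of cumulative safety data. A reader might also infer that the error rate is doubled. Nothing says that directions will be chosen late, and the redacted 16.5.2 and 16.5.3 may fix them.

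Some example variables will be thinner than the assumed sizes. CBC, chemistry and clotting times in controls are taken only if standard of care (16.3, note h), as are CBC and chemistry from Day 0 onwards in Arm 2 (Section 1, note v). So 24 v 12 may be an upper bound for them. Section 7.2.2.3 also adds that thromboembolic events were rare and not significantly different from control. That weakens the prior concern about D-dimer, but it is no reason to test in one direction only.

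**Conclusion.** The point holds in a limited form. A blanket one-sided rule leaves every continuous variable with one direction in which a treated–control difference cannot be declared, and several of the scheduled markers matter in both directions. This follows from the test itself and rests on no assumption about sample size or redacted text. The contrast with two-sided power (78.5% for a 1.0 SD shift at 24 v 12; 64.9% at 12 v 12; 92.4% at 24 v 24) does rest on an assumed two-sided 5% level and assumed group sizes.

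The consequence is confined to how this secondary, non-randomised comparison is reported. It does not reach the MTD, the dose-escalation rules or the safety tables. The doubled error rate is only a caution against choosing a direction late. The change is worth making because it is cheap; the point does not threaten the trial's primary conclusions.

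**What to change.** In Section 16.5.1, replace the one-sided test with a sentence to this effect: *for each continuous variable, the estimated treated-minus-control difference in means will be reported with a two-sided 95% confidence interval.* If the sponsor wants to keep 5% in the tail for benefit, use a two-sided 90% interval, which shows movement either way equally. The sentence should state the level chosen.

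The alternative is to pre-specify a direction and level for each variable. That would settle the question of late choice, but it would leave the untested side of each variable unreported, so intervals are preferable.

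The change costs one sentence, with no new patients, visits or samples. If the intended one-sided level is 5%, a two-sided 5% analysis lowers power for a 1.0 SD benefit from 87.0% to 78.5% at the assumed 24 v 12. If the intended level is 2.5%, there is no loss. A 90% interval also loses nothing for benefit, at the price of a nominal two-sided error of 10%.

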16.5.2 CLINICAL END-POINTS

[REDACTED]
n Day 28. The scale reflects patient trajectory

16.5.3 BIOMARKER ANALYSIS

[REDACTED]
